## **12 DISCONTINUATION AND REPLACEMENT OF SUBJECTS**

### **12.1 Early Discontinuation of Study Drug**

A subject may be discontinued from study treatment at any time if the subject, the investigator, or the Sponsor feels that it is not in the subject's best interest to continue. The following is a list of possible reasons for study treatment discontinuation:

- Subject withdrawal of consent (or assent)
- Subject is not compliant with study procedures
- Adverse event that in the opinion of the investigator would be in the best interest of the subject to discontinue study treatment
- Protocol violation requiring discontinuation of study treatment
- Lost to follow-up
- Sponsor request for early termination of study
- Positive pregnancy test (females)

If a subject is withdrawn from treatment due to an adverse event, the subject will be followed and treated by the Investigator until the abnormal parameter or symptom has resolved or stabilized.

All subjects who discontinue study treatment should come in for an early discontinuation visit as soon as possible and then should be encouraged to complete all remaining scheduled visits and procedures.

All subjects are free to withdraw from participation at any time, for any reason, specified or unspecified, and without prejudice.

Reasonable attempts will be made by the investigator to provide a reason for subject withdrawals. The reason for the subject's withdrawal from the study will be specified in the subject's source documents. Refer to Section 10 for early termination procedures.

## 12.2 Withdrawal of Subjects from the Study

A subject may be withdrawn from the study at any time if the subject, the investigator, or the Sponsor feels that it is not in the subject's best interest to continue.

All subjects are free to withdraw from participation at any time, for any reason, specified or unspecified, and without prejudice.

Reasonable attempts will be made by the investigator to provide a reason for subject withdrawals. The reason for the subject's withdrawal from the study will be specified in the subject's source documents. As noted above, subjects who discontinue study treatment early (i.e., they withdraw prior to Visit 4) should have an early discontinuation visit. Refer to Section 10 for early termination procedures. Subjects who withdraw after Visit 3 but prior to Visit 4 should be encouraged to come in for a final visit (and the procedures to be followed would include those for their next scheduled visit).

## 12.3 Replacement of Subjects

We plan to enroll 60 participants to consent 50.

Subjects who withdraw from the study treatment will not be replaced.

Subjects who withdraw from the study will not be replaced.

## 13 PROTOCOL VIOLATIONS

A protocol violation occurs when the subject, investigator, or investigator fails to adhere to significant protocol requirements affecting the inclusion, exclusion, subject safety and primary endpoint criteria. Protocol violations for this study include, but are not limited to, the following:

Failure to meet inclusion/exclusion criteria

Use of a prohibited concomitant medication

Failure to comply with Good Clinical Practice (GCP) guidelines will also result in a protocol violation. The PI will determine if a protocol violation will result in withdrawal of a subject.

When a protocol violation occurs, it will be discussed with the investigator and a Protocol Violation Form detailing the violation will be generated. This form will be signed by a Sponsor representative and the Investigator. A copy of the form will be filed in the site's regulatory binder and in the Sponsor's files.

## 14 DATA SAFETY MONITORING

Safety Data Monitoring throughout the trial: Since this trial is a single-site trial and the overseeing Principle Investigator will be present throughout the trial, a Data and Safety Monitoring Board is not deemed necessary. The study investigator will be responsible for monitoring safety data and adverse events recorded in the patient file and will be responsible for reporting such events to the FDA and IRB.

Safety assessments will be throughout patient visits to ensure patient welfare and safety in daily activities.

Such assessments will include:

- Physical Examination
- Vital Signs
- Height and Weight measurements
- Pregnancy and Assessments of Fertility
- Ophthalmologic Examination

- Fatigue Assessment - Health Status Questionnaire & MFIS
- Pharmacokinetics/Blood tests to assess potential abnormal increase of liver enzymes and serum triglycerides
- Lab tests to assess level of BZA in patient plasma to ensure that they are not abnormal

The Investigator will meet with the study staff biweekly to review safety as well as efficacy data collected from patient visits and assess the safety of the visits and study outcomes.

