### **Pharmacokinetics/Lab Tests**

Participant's serum and PBMCs will be properly stored for later analysis (if needed).

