#### **9.2.2 Blood Chemistry Profile**

Blood will be obtained and sent to each site's clinical chemistry lab for determination of serum sodium, potassium, chloride, bicarbonate, random glucose, BUN, creatinine, aspartate aminotransferase (AST/SGOT), alanine aminotransferase (ALT/SGPT), alkaline phosphatase, total bilirubin, direct bilirubin.

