## **10 EVALUATIONS BY VISIT**

### **10.1 Visit 1 (Week 0) - Screening**

1. Review the study with the subject and obtain written informed consent and HIPAA authorization and assent, if appropriate.
2. Assign the subject a unique screening number.

3. Record demographics data.
4. Record medical history, including a history of MS, diagnosis date, and prior MS treatments, as well as history of optic neuritis.
5. Record concomitant medications.
6. Perform a complete physical examination.
7. Perform VEP and OCT assessments (if no record of assessment within past 6 months)
8. Perform and record vital signs.
9. Perform and record results of blood pressure testing.
10. Collect blood for clinical laboratory tests (chemistry, hematology, pregnancy test)
11. Initiate subject diary
12. Schedule subject for Visit 2 in 14 days +/-2.

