### 10.3 Visit 3 (3-month)

1. Record any Adverse Experiences and/or Review subject diary for adverse experiences and dosing compliance.
2. Record changes to concomitant medications.
3. Perform abbreviated physical examination.
4. Assess likely side effects via clinician observation and questionnaires
5. Perform and record vital signs.
6. Collect blood for research laboratory tests (if needed)
7. Perform neurologic and ophthalmologic exam.
8. Perform and record visual assessments (high/low contrast vision testing, cone contrast, VFQ)

9. Perform and record cognitive & other tests (SDMT, MFIS, EDSS, SF-36)
10. Perform timed walking tests (T25W, TUG, 6 min walking test)
11. Perform MRI (no contrast)

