**Patient withdrawal from the study / Stopping rules:**

Study treatment must be discontinued for any patient if the investigator determines that continuing would result in a significant risk for that patient. The following conditions/events may be considered sufficient to support a decision about the study drug discontinuation in individual cases:

- Adverse event/serious adverse event
- Abnormal laboratory value(s) or abnormal test result(s)
- Withdrawal of informed consent
- Pregnancy
- Use of prohibited other investigational medications
- Deviations from the prescribed dose regimen for the study drug
- Any other protocol deviation that results in a significant risk to the patient's safety

Discontinuation of the study drug must be recorded along with the patient information in REDCap, giving the date and primary and secondary reasons for stopping study treatment. The investigator must also contact the Institutional Review Board at the study site (University of California at San Francisco Multiple Sclerosis Center) to register the patient's discontinuation of randomized study drug.

Patients may voluntarily withdraw from the study for any reason at any time. They may be considered withdrawn if they state an intention to withdraw, fail to return for visits, or become lost to follow-up for any other reason.

For patients who are lost to follow-up (i.e. those patients whose status is unclear because they fail to appear for study visits without stating an intention to withdraw), the investigator should show "due diligence" by documenting in the source documents steps taken to contact the patient, e.g. dates of telephone calls, registered letters, etc.

If premature withdrawal occurs for any reason, the investigator must make every effort to determine the primary reason for a patient's premature withdrawal from the study and record this information with the patient's research data in REDCap as well as report this withdrawal to the Institutional Review Board and FDA CDER, if deemed necessary by the committee.

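### No liver chemistry is scheduled between Screening and Month 6, and the triglycerides named in the safety monitoring plan are not in the panel at any visit

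*Combined protocol and SAP*

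**What the plan says.** Section 14 introduces its monitoring list with "Safety assessments will be throughout patient visits". The list includes "Blood tests to assess potential abnormal increase of liver enzymes and serum triglycerides". The stopping rules that follow include "Abnormal laboratory value(s) or abnormal test result(s" among events that may be enough to support stopping study drug in an individual case. The same section dispenses with a data and safety monitoring board and gives safety review to the investigator, who meets study staff every two weeks.

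The visit plan places the chemistry as follows.

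- Screening (section 10.1): chemistry, hematology and a pregnancy test. The next step there is "Schedule subject for Visit 2 in 14 days +/-2".
- Baseline (section 10.2): research blood only.
- Month 3 (section 10.3): the only blood item is "Collect blood for research laboratory tests (if needed". Section 9.1.6 says that such samples are stored for possible later use.
- Month 6 (section 10.4): chemistry and hematology.
- Early withdrawal (section 10.5): chemistry and hematology.

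Appendix 1 agrees on chemistry, marking it at Screening and Month 6 only. It marks hematology at Screening, Month 3 and Month 6, so section 10.3 leaves out a hematology draw that the schedule requires.

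Section 9.2.2 defines the panel. It contains AST and ALT and ends with "alkaline phosphatase, total bilirubin, direct bilirubin". Triglycerides are not in it.

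**The concern.** The monitoring section relies on laboratory values to protect participants during dosing, but the schedule provides no liver value until dosing is over. A rise in AST or ALT without symptoms would have no scheduled test to reveal it, and the two-weekly review cannot consider a result that was never drawn. The plan treats liver function as relevant to eligibility: exclusion 17 sets a limit of 2 times the upper limit of normal for AST, ALT and alkaline phosphatase, and exclusion 30 bars known hepatic impairment.

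The second issue is interpretation. Documenting safety is the third key secondary objective (section 3.2), and safety data are summarised by treatment group (section 15.4). Placebo is given only to Group B in the first 90 days (section 4.1). By Month 6 both groups have had bazedoxifene, and background MS therapy continues in both. The only post-baseline chemistry therefore has no placebo group beside it.

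**Working it through.** The plan gives no figure to reproduce here. The check compares the schedule with the monitoring section and adds up the intervals.

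**Inputs.** Screening to Baseline is 14 days, plus or minus 2 (section 10.1). Drug is dispensed at Baseline (section 10.2, Appendix 1). Stage 1 is 90 days and Stage 2 is 90 days (section 4.1). There are 25 participants per group (section 15.6). I take Visits 3 and 4 at days 90 and 180 after Baseline, because no windows are given for them.

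**Scheduled chemistry draws for a participant who stays in:** Screening 1, Baseline 0, Month 3 0, Month 6 1. Triglyceride measurements in the listed panel: 0 at any visit.

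**Interval between scheduled chemistries:** 12 + 180 = 192 days to 16 + 180 = 196 days.

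**Age of the last AST/ALT when Group B takes its first bazedoxifene dose:** 12 + 90 = 102 days to 16 + 90 = 106 days.

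**Bazedoxifene exposure before the first scheduled post-baseline chemistry:** 180 days in Group A and 90 days in Group B.

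**Scheduled chemistry on placebo:** 0 of 25.

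**With the panel added at Visit 3:**

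- The Screening-to-Visit-3 interval is 102 to 106 days, followed by 90 days to Month 6.
- The longest bazedoxifene run without a draw falls from 180 to 90 days.
- Group B starts bazedoxifene with a sample taken at the same visit. The result may not be known by the first dose, because Appendix 1 dispenses drug at that visit.

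**What a Visit 3 comparison could show**, with 25 on bazedoxifene and 25 on placebo at most:

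- Mean change from Screening: the 95% confidence half-width is t(0.975, 48) × √(2/25) = 2.011 × 0.283 = 0.57 SD.
- Outliers: if 10% on bazedoxifene and 1% on placebo had a marked rise (assumed rates, as the documents give none), Fisher's exact test at two-sided 0.05 has power of about 2.8%.
- No events among 25: the two-sided 95% upper limit is 1 − 0.025^(1/25) = 13.7%.

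**The case against.** The strongest reply is that section 14 does not promise a liver test at each visit. Its list also names height and pregnancy assessment, and Appendix 1 schedules height and the pregnancy test at Screening only. Section 9 makes Appendix 1 the schedule of required procedures. Liver enzymes at Screening and Month 6 are therefore compatible with a literal reading of section 14. This stands: for AST and ALT the point is a gap in monitoring, not a contradiction. The document errors proper are the missing triglycerides and the hematology omitted from section 10.3.

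A reader might infer that Visit 3 is the last chance to change a participant's dosing. It is not. Section 12.1 lets study drug be stopped at any time, unscheduled tests are possible, and section 8.4.2 allows resupply between visits. What remains is that no scheduled liver result would prompt such a stop. The early-withdrawal draw does not fill the gap, because it follows the decision to leave.

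A reader might also infer that a Visit 3 panel would detect drug-related liver harm with some stated probability, or would settle whether bazedoxifene raises liver enzymes. The documents give no rate of elevation. Any assumed rate could equally describe chance elevations, and a comparison of 25 with 25 says very little about outliers.

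The plan also cites substantial 40 mg experience: 840 women in one trial and 1,872 in another (section 1.2). That argues against frequent monitoring, but not against one draw at an existing visit.

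Finally, stored serum might allow a retrospective comparison between groups. That is possible, but the visit text makes collection conditional, the plan does not commit to any assay, and a later result cannot guide a participant's dosing.

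**Conclusion.** The point holds as a low-cost improvement to safety monitoring, together with two document corrections. A participant who follows the schedule has no AST or ALT for 192 to 196 days. Group A completes 180 days of bazedoxifene, and Group B starts it on a value 102 to 106 days old. During dosing, the laboratory stopping criterion has no scheduled liver value to act on, although the Month 3 hematology in Appendix 1 can still inform it. No scheduled chemistry falls in the placebo-controlled period, and triglycerides are named in the monitoring plan but not measured in the listed panel.

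These figures rest on the protocol's own timings, with Visits 3 and 4 taken at days 90 and 180, and apply to participants who do not withdraw. The case for the extra draw is individual safety. The comparison between groups that it would also provide is descriptive and should be labelled so. Exclusion 17 is an entry limit, and the documents do not support turning it into a mandatory rule for withholding drug.

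**What to change.** 1. Draw the section 9.2.2 chemistry panel at Visit 3. Mark it in Appendix 1 and list it in section 10.3, together with the hematology that Appendix 1 already requires there.
2. Add triglycerides to section 9.2.2, or delete them from section 14.
3. State in section 14 that the investigator reviews the Visit 3 result promptly and repeats the test for any clinically significant rise, judged against the participant's own screening value, in either group and without unblinding. As drug is dispensed at that visit, the participant is telephoned if a result that needs action arrives later.
4. Report Visit 3 chemistry by treatment group as a descriptive summary.

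The cost is about 50 panels at a visit where Appendix 1 already schedules hematology and research blood, plus a few sentences of text. An occasional false flag is likely: if 1% to 5% of participants showed a rise by chance (assumed), that is 50 × 0.01 = 0.5 to 50 × 0.05 = 2.5 people. Any interruption of dosing would come after the 90-day primary VEP period, so it could affect only the 180-day comparison.

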### 4 STUDY DESIGN

#### 4.1 Study Overview

This is a 6-month randomized, single center, double blinded, delayed start study in 50 patients with relapsing remitting multiple sclerosis and identified injury to the anterior visual pathway.

Patients will be randomized 1:1 into two groups: Group A and Group B. Group A will receive 180 days of Bazedoxifene while Group B will receive 90 days of placebo followed by 90 days of Bazedoxifene. Patients will receive two fixed oral tablets of 20mg Bazedoxifene (Conbriza) daily (to be taken at the same time). Patients will be permitted to remain on their standard disease modifying treatment during the course of the study.

Screening data will be reviewed to determine subject eligibility. Subjects who meet all inclusion criteria and none of the exclusion criteria will be entered into the study

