## 8.2 Blinding

Due to the objectives of the study, the identity of test and control treatments will not be known to investigators, research staff, or patients. The following study procedures will be in place to ensure double-blind administration of study treatments.

- Access to the randomization code will be strictly controlled.
- The CTSI statistician advising the PI will perform the randomization/blinding chart and provide this to the Compounding Pharmacy. They will perform interim safety analysis without unblinding the study, and will only unblind the study to the investigators at the end of study.
- Packaging and labeling of test and control treatments will be identical to maintain the blind.
- Packaging and labeling will be done by pharmacy personnel who are not involved in analysis of study data.

The study blind will be broken on completion of the clinical study and after the study database has been locked. The investigators will be given the randomization worksheet from the CTSI statistician after the last participant has completed their study.

During the study, the blind may be broken **only** in emergencies when knowledge of the patient's treatment group is necessary for further patient management. When possible, the Investigator should discuss the emergency with [name] prior to unblinding.

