### 8.3.2 Formulation of Control Product

Placebo is: Microcrystalline cellulose, encapsulated into a gelatin capsule, taken daily.

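### Section 14 lists a BZA plasma level as a during-trial safety check under a blinded investigator, while Section 8.2 does not withhold levels and no visible schedule names the assay

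*Combined protocol and SAP*

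**What the plan says.** **Section 14 (Data Safety Monitoring).** The list of safety assessments ends with "Lab tests to assess level of BZA in patient plasma to ensure that they are not abnormal". It is introduced by "Safety assessments will be throughout patient visits to ensure patient welfare and safety in daily activities". The section dispenses with a DSMB and states that "The study investigator will be responsible for monitoring safety data and adverse events recorded in the patient file". It then adds: "The Investigator will meet with the study staff biweekly to review safety as well as efficacy data collected from patient visits".

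**Section 8.2 (Blinding).** The rule is that "the identity of test and control treatments will not be known to investigators, research staff, or patients". Apart from the end of the study, the blind may be broken only "in emergencies when knowledge of the patient's treatment group is necessary for further patient management".

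**Sections 4.1 and 8.3.2.** The groups differ in Stage 1 only: "Group B will receive 90 days of placebo followed by 90 days of Bazedoxifene", and the placebo is "Microcrystalline cellulose, encapsulated into a gelatin capsule, taken daily".

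**Section 9.1.6 (Pharmacokinetics/Lab Tests).** This provides only for keeping serum and PBMCs in store, to be analysed later should the need arise. It names no assay, no analyte and no time point, and it does not mention plasma.

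**The concern.** In a placebo-controlled stage, a drug level is close to an allocation code. Section 14 puts that level on the safety list of the people whom Section 8.2 requires to be blinded, and no visible text keeps the result from them. If Section 14 is followed as written before database lock, the blind can be lost through an ordinary laboratory report. If the storage-only text in Section 9.1.6 is followed instead, the blind is safe but a listed safety check is not carried out. The two sections cannot both be followed as written.

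Section 5.2.2 names a blinded physician for assessing MRI. Section 5.1 names no separate masked reader for the VEP traces, so the primary outcome measure depends on the general blind in Section 8.2. The first key secondary objective (Section 3.2) compares the groups at 180 days. Those data are collected after a Month-3 level could have become known.

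**Working it through.** The plan gives no figure to reproduce here. The check sets the sections side by side.

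**1. When would a level separate the groups?** Appendix 1 stores research blood at all four visits.

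| Visit | Group A | Group B | Does a level separate the groups? |
|---|---|---|---|
| Screening | no study drug | no study drug | no |
| Baseline (first dispensing) | no study drug yet | no study drug yet | no |
| Month 3 (end of Stage 1) | BZA | placebo | yes |
| Month 6 (end of Stage 2) | BZA | BZA | not by design |

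Month 3 is the informative sample. A detectable level there identifies Group A: exclusion 16 bars other putative remyelinating therapy, including the BZA-containing product Duavée, so another source is unlikely. An undetectable level means Group B or a non-adherent Group A patient, so it strongly suggests Group B without proving it. With 1:1 allocation of 50 patients, 25 + 25 = 50 could be affected if every patient were assayed.

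**2. Who would see the result?** No sentence says outright that individual BZA levels go to the investigator. Three provisions point that way:
- Section 14 makes the investigator the monitor of safety data and sets up the joint review with staff.
- The stopping rules in Section 14 count abnormal laboratory or test results among the grounds on which study drug may be stopped in an individual case, which presupposes individual results.
- Section 16.1 has the investigator review and verify all study data.

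**3. What stands in the way?** Section 8.2 has four bulleted safeguards: control of access to the code; the CTSI statistician's handling of the randomization chart, interim safety analysis and final unblinding; identical packaging; and packaging by pharmacy staff uninvolved in analysis. None mentions drug levels (0 of 4).

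**4. Is the assay ordered anywhere?** The procedure lists are 9.2.1 and 9.2.2 (2), Visits 1 to 4 (4) and Early Withdrawal (1): 2 + 4 + 1 = 7. A BZA assay is named in 0 of 7. Appendix 1 has 31 rows and names it in 0 of 31. The abbreviation list defines HPLC-MS/MS, but the visible text does not use it.

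**5. What could be influenced?** Appendix 1 places VEP and stored research blood at the same Month-3 visit, so the Month-3 recording would ordinarily precede any assay result. What remains open is later reading of the Month-3 traces, judgements of adverse-event causality, and the Day-180 comparison of Group A with Group B.

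**The case against.** The strongest reply is that the Section 14 list is a loose inventory and not an order. It also lists height, weight and pregnancy assessment, which Appendix 1 schedules at screening only, and serum triglycerides, which the chemistry panel in Section 9.2.2 omits. On that view one bullet does not instruct anyone to report Stage 1 levels. Research blood is stored at every visit, Visits 2 to 4 allow research laboratory tests if needed, and a later assay of stored samples leaves the blind intact. Section 8.2 also has safety analysis proceed without unblinding and keeps allocation from investigators until the end of the study, which any safety assay would have to respect.

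Much of this stands. The timing and routing of the assay are inferred, and Section 8.2 does state a general rule; what it lacks is an operating instruction for a result that reveals allocation. But the storage reading contradicts Section 14's description of a check made during visits, and it names serum and PBMCs where Section 14 names plasma. The inconsistency remains on either reading.

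A reader might infer more than the documents support:
- That the trial will be, or was, unblinded. No text shows a level being reported to the blinded team.
- That acquisition of the primary 90-day VEP is compromised. The recording and the blood sample belong to the same visit.
- That early withdrawals add a second exposed sample. Section 10.5 draws only chemistry and hematology.
- That the number of review meetings measures the harm. Once a level has been seen, further meetings add nothing to the knowledge of allocation.

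**Conclusion.** The conflict holds and should be fixed. Section 14 lists a during-trial BZA level under a blinded investigator, Section 8.2 does not withhold levels, Section 9.1.6 only stores samples, and no visible procedure list or schedule row names the assay.

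The size is a count of exposure: one informative scheduled sample, at Month 3, in up to 50 patients. No bias can be computed, because the documents give no VEP variance and do not say how levels would be used.

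The conclusion assumes that the assay detects BZA during daily dosing (no assay limit is given), that the Month-3 sample is drawn before any Stage 2 dose, and that results would reach the investigator by the routes in Sections 14 and 16.1. Confidence is moderate. The text available for this review lacks the part after Section 11.2.1, where the contents page places 11.3 Medical Monitoring, and the study manual was not available. Either could contain a routing rule.

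**What to change.** Reconcile Sections 8.2, 9.1.6, 10 and 14 and Appendix 1 so that no individual BZA level reaches the investigator, study staff or the joint safety and efficacy review before database lock. There are two ways to do this, and the sponsor should choose one.

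- **Assay after lock.** State that BZA is measured only in stored samples after database lock, and remove the level from the during-trial list in Section 14. The cost is that the listed during-trial check is given up.
- **Assay during the trial, outside the blinded team.** Add the sample and visit to Section 10 and Appendix 1. Route individual levels only to an existing code holder outside the blinded team, such as the CTSI statistician. State who outside that team reviews the levels, and that any disclosure follows the emergency unblinding provision already in Section 8.2. The cost is a laboratory-routing instruction and an unblinded person to do the review.

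The second option also requires settling who performs the interim safety analysis: Section 8.2 appears to give it to the CTSI statistician, whereas the Synopsis and Section 15.5 give it to the PI. Under either option, make the sample type agree between Section 14 (plasma) and Section 9.1.6 (serum and PBMCs). Neither option adds patients or visits.
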